## 7.3 Sample size

The sensitivity and specificity of the Abbott RealTime HCV assay on dried blood spot samples will be compared with the Abbott RealTime HCV assay on plasma samples collected via venepuncture. Assuming an SVR of 95%, (n=100, one sample at BL and SVR12, total n=200), a sensitivity and specificity of 95%, 200 samples would provide a 95% confidence interval of 89-98% for the estimates of sensitivity and specificity. Assuming an SVR of 95%, (n=150, one sample at BL and SVR12, total n=300), a sensitivity and specificity of 95%, 300 samples would provide a 95% confidence interval of 90-98% for the estimates of sensitivity and specificity. Assuming an SVR of 95%, (n=200, one sample at BL and SVR12, total n=400), a sensitivity and specificity of 95%, 400 samples would provide a 95% confidence interval of 91-98% for the estimates of sensitivity and specificity.

The sample size for the study is n=200 patients (n=400 samples) to provide a sensitivity/specificity of 95% with a 95% CI of 91-98%.

## 7.4 Statistical methodology

Descriptive analyses will be performed to characterise the study population including median (interquartile range) or mean (SD). Patient population will be described by age, sexual orientation, education, income, liver disease stage (categorised by APRI), drug and alcohol use, daily functioning and HIV parameters as well as HCV related parameters including HCV genotype and viral load. Continuous variables will be summarised by either mean and standard deviation (SD) or median and interquartile range (IQR), as appropriate.

Factors associated with knowledge of liver disease will be assessed using logistic regression analyses. Variables hypothesized to be associated with HCV knowledge to be assessed in unadjusted analyses will include: sex, age, education, accommodation, employment, social functioning, injecting drug use, alcohol use and HCV infection status. All variables with p<0.20 in bivariate analysis will be considered in multivariate logistic regression models using a backwards stepwise approach sequentially eliminated subject to the result of a likelihood ratio test. Statistically significant differences will be assessed at p<0.05 (two-sided p-values).

Proportion of participants achieving SVR will be calculated. SVR12 will be defined as HCV RNA target not detected (TND) or target detected, not quantifiable (TD, nq) at post-treatment week 12. For the efficacy endpoint, means and proportions with two-sided 95% confidence intervals (CI) will be determined. Categorical data will be analysed using the Chi squared or Fisher's exact test. Continuous variables will be analysed using the t-test or the Mann-Whitney U test, as appropriate.

Logistic regression analysis will be used to identify factors associated with SVR. Potential predictors will be determined *a priori* and will include age, gender, liver disease stage (categorised by APRI), drug use and alcohol use, CD4 count and HIV RNA.

The multivariate models will be determined using a backwards stepwise approach, considering factors that were significant at the 0.2 level in univariate analysis. The final models will include factors that remain significant at the 0.05 level. All statistical tests will be two-sided with a significance level of 0.05. Analysis will be performed using STATA (version 14.0; Stata Corporation, College Station, TX).

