#### 3.2 Secondary objectives

- 1) To evaluate acceptability and feasibility of DBS collection in Myanmar.
- 2) To evaluate concordance pre and post therapy between HCV RNA (fingerstick) and standard plasma HCV RNA detections.
- 3) To evaluate concordance pre and post therapy between HCV core antigen (DBS) and standard plasma HCV RNA detections.
- 4) To evaluate concordance pre and post therapy between HCV RNA (DBS) and standard plasma HCV RNA detections.
- 5) To evaluate patients' knowledge on HCV by using set-up questionnaire.
- 6) To understand HCV virus patterns in Myanmar through phylogenetic sequencing.
- 7) To enhance and develop laboratory and research capacity at Specialist Hospital Mingaladon (SHM), Specialist Hospital Waibargi (SHW) and Insein General Hospital (IGH).

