#### **6.7 Questionnaires**

All participants will complete a questionnaire at baseline and at SVR12. Questionnaires will be completed on paper or electronically on tablet. Study staff will be available to assist participants to complete this questionnaire as required.

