## a) The Behavioral Questionnaire

The behavioral survey will collect information on the following:

- Demographics
- Injecting and alcohol
- Drug treatment history
- Hepatitis C testing and treatment knowledge
- Quality of life

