# 7.2 Secondary endpoints

- Sensitivity and specificity of HCV RNA on GeneXpert machine using capillary blood collected via fingerstick compared to standard HCV RNA plasma tests
- Sensitivity and specificity of HCV RNA on DBS compared to standard HCV RNA plasma tests
- Sensitivity and specificity of HCV core antigen on DBS compared to standard HCV RNA plasma tests
- Proportion of patients identified with active HCV viremia at screening
- Change in HIV RNA/T cell count pre and post therapy
- Change in liver function tests and APRI score pre and post therapy
- Knowledge of the patients on HCV testing and treatment

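### Protocol 7.4 fixes logistic regression for a questionnaire-based HCV-knowledge endpoint that has no stated yes/no event; if the knowledge section yields a score, cutting it costs power that whole-score analysis would keep

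*Protocol*

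**What the plan says.** Protocol 3.2 sets the objective: "To evaluate patients' knowledge on HCV by using set-up questionnaire". Protocol 7.2 lists the endpoint as "Knowledge of the patients on HCV testing and treatment". The instrument is the behavioural survey in 6.7, in which "Hepatitis C testing and treatment knowledge" is one of five domains. On timing, 6.7 says: "All participants will complete a questionnaire at baseline and at SVR12". The protocol does not give the number of items, the scoring, or a definition of being knowledgeable.

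Protocol 7.4 fixes the analysis: "Factors associated with knowledge of liver disease will be assessed using logistic regression analyses". It then sets the model building: "All variables with p<0.20 in bivariate analysis will be considered in multivariate logistic regression models using a backwards stepwise approach", with elimination by likelihood ratio test, and "Statistically significant differences will be assessed at p<0.05 (two-sided p-values". The sentence that lists candidate variables calls the outcome HCV knowledge, although the sentence before it speaks of liver disease. Later in 7.4 the same term, logistic regression, is used for factors associated with SVR.

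**The concern.** The term logistic regression without qualification normally means a model for a yes/no outcome. SVR has a natural event. A knowledge domain in a questionnaire usually does not, and the protocol names none. If the domain produces a count of correct answers, following 7.4 means splitting patients into two classes and ignoring differences within each class.

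This is a stated choice of method, so it differs from a detail left to the SAP. A SAP that follows 7.4 could supply the cut, but it could not recover the information that the cut discards. At stake is the chance of detecting real correlates of knowledge, such as education or injecting drug use, with 200 patients. The wording adds a smaller problem: knowledge of liver disease is a different construct from knowledge of HCV testing and treatment, and the model sentence names the former.

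**Working it through.** **Inputs from the protocol.** n = 200 (7.3: "The sample size for the study is n=200 patients (n=400 samples"); two-sided 0.05 and the likelihood ratio test (7.4).

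**Assumed, not in the protocol.** A binary factor, a true difference d of 0.4 or 0.5 SD, a normal score with SD 1 in each group (or a 10-item count), the factor split, and the cut.

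**1. The plan's own figure.** The only precision statement is the 91-98% interval around 95% sensitivity or specificity. The exact (Clopper-Pearson) interval for 190/200 is 91.0-97.6%, so it reproduces. It concerns the assays. No power is stated for knowledge, so n = 200 is taken as given.

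**2. Score kept whole, 100 v 100.** Power = Φ(d/√(1/100 + 1/100) − 1.96).
- d = 0.4: 0.4/0.1414 = 2.828; Φ(0.868) = 80.7%.
- d = 0.5: 0.5/0.1414 = 3.536; Φ(1.576) = 94.2%.

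**3. Score cut at the median, d = 0.4.** The shares above the cut are Φ(−0.2) = 0.421 and Φ(0.2) = 0.579, a difference of 0.1585. The pooled SE is √(2 × 0.25/100) = 0.0707 and the unpooled SE is √(2 × 0.421 × 0.579/100) = 0.0698. Power = Φ((0.1585 − 1.96 × 0.0707)/0.0698) = Φ(0.285) = 61.2%. The loss is 80.7 − 61.2 = 19.5 points.

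The same formula at other cuts, 100 v 100 (losses from unrounded powers):

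| Cut | Power (loss), 0.4 SD | Power (loss), 0.5 SD |
|---|---|---|
| none | 80.7% | 94.2% |
| 50/50 | 61.2% (19.5) | 80.2% (14.0) |
| 70/30 | 56.6% (24.2) | 75.5% (18.7) |
| 75/25 | 53.6% (27.1) | 72.3% (21.9) |
| 80/20 | 49.5% (31.2) | 67.7% (26.5) |
| 90/10 | 36.2% (44.6) | 50.7% (43.5) |

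**4. Simulation with the test the plan names.** The formula is a normal approximation, so the t-test on the score was also set against the likelihood ratio test on the cut score (4,000 runs; Monte Carlo SE of each power at most √(0.25/4000), about 0.8 points).
- 0.4 SD: median 79.8% v 63.4% (16.4 points lost); 70/30 80.2% v 57.9% (22.3); 75/25 79.1% v 54.4% (24.7).
- 0.5 SD: median 93.3% v 81.1% (12.2); 70/30 94.5% v 77.3% (17.2); 75/25 93.9% v 73.3% (20.6).

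A 10-item count score (3,000 runs), median and top-quartile cuts:
- 50/50 factor, 0.4 SD: 69.3% v 53.9% (15.4) and 68.2% v 47.8% (20.4).
- 25/75 factor, 0.5 SD: 76.1% v 59.9% (16.2) and 74.7% v 55.3% (19.4).

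A further simulation of continuous and 10-item scores at 0.4-0.5 SD gave losses of about 10-22 points. Taken together, the likelihood ratio results run from roughly 10 to 24 points, up to Monte Carlo error.

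**5. Where the loss is larger.** Besides the 80/20 and 90/10 rows above, unequal factor groups can raise it. For cuts from the median to 70/30, the formula gives 17-28 points at 140/60 and 19-32 at 160/40. Those runs put the more knowledgeable patients in the smaller group and most patients above the cut, which is an unfavourable arrangement.

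**6. Where the loss is small or absent.** With a single yes/no item the two analyses coincide. For a 10-item score made mostly of easy items and cut at all correct, one simulation gave the whole score 41% against 43% for the cut at 0.4 SD, and 55% against 60% at 0.5 SD. A three-item easy score gave 46% against 44% at 0.4 SD. Other simulations of an easy-item score lost about 8-14 points, so under a ceiling the answer depends on the instrument and the cut.

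All of these are single-factor tests. The full screen-and-eliminate procedure was not simulated.

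**The case against.** The strongest objection is that the protocol never says knowledge is a score. It lists a questionnaire topic and an endpoint, with no items or total. If the outcome is one yes/no item, or items are modelled one at a time, logistic regression is the natural method and nothing is lost. This stands, and it makes the loss conditional. It does not remove the point: a domain covering testing and treatment more likely has several items, and 7.4 makes no provision for that case.

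Second, ordinal logistic regression is also logistic regression and also uses likelihood ratio tests. That is fair. But 7.4 does not say ordinal, and it uses the same bare term for SVR. If ordinal was meant, one word settles it.

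Third, a reader might infer that the threshold will be picked after the data are seen, so that the factors found depend on a post-hoc choice. The protocol does not show that. Scoring rules and cuts are commonly fixed in a SAP, which is not at hand, and their absence from the protocol is not a fault.

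Fourth, a reader might infer that every cut does worse than the whole score. That is not so as a general statement: the easy-item example cut at all correct did slightly better than the total.

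Finally, no objective names determinants of knowledge, and the study is sized on sensitivity and specificity. That is correct, and it limits the weight of the point.

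**Conclusion.** The point holds in conditional form. Protocol 7.4 specifies what is ordinarily a binary-outcome model for a questionnaire endpoint with no stated yes/no event, and it names the outcome inconsistently. If the knowledge section yields a reasonably spread score, dichotomising it at n = 200 costs roughly 10-24 points of power. This assumes differences of 0.4-0.5 SD, cuts from the median to the top quartile, and a factor split 50/50 or 25/75. The normal-approximation formula, more extreme cuts and unfavourable unequal splits give larger losses. A single yes/no item loses nothing, and a strongly ceilinged score may lose little or nothing.

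A reader might take the 10-24 points as the cost of the plan as written. It is not: effect size, distribution, factor split and cut are all absent from the protocol. The analysis is exploratory and secondary, and neither SVR12 nor the sensitivity and specificity endpoints are affected. This is a minor improvement.

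**What to change.** In 7.4, name the outcome HCV testing and treatment knowledge throughout, in line with 7.2 and the questionnaire domain in 6.7. State that, where the knowledge section yields a total score, associated factors will be assessed on the whole score by linear regression with robust standard errors, or by proportional-odds (ordinal logistic) regression if the score has few levels, with adjusted effects and 95% confidence intervals. Keep any high/low proportion as a descriptive summary with a pre-specified cut. Keep binary logistic regression only if the outcome is a single yes/no item.

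The cost is a change of wording: same questionnaire, patients and software. The downside is that results appear as score differences or common odds ratios instead of odds of adequate knowledge, which some readers find easier to interpret.

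### Section 7.4 picks HCV-knowledge factors by p-value and estimates them from the same data, so the odds ratios it retains are exaggerated (minor)

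*Protocol*

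**What the plan says.** Patient knowledge is a secondary endpoint in Protocol section 7.2: "Knowledge of the patients on HCV testing and treatment". Section 7.4 analyses it by logistic regression and fixes the model-building rule:

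- **Candidates.** Nine variables are named: "sex, age, education, accommodation, employment, social functioning, injecting drug use, alcohol use and HCV infection status". They are introduced as hypothesised correlates of knowledge, each to be examined unadjusted first.
- **Screen.** "All variables with p<0.20 in bivariate analysis will be considered in multivariate logistic regression models using a backwards stepwise approach".
- **Elimination.** Variables are "sequentially eliminated subject to the result of a likelihood ratio test". The knowledge paragraph gives no threshold for this step, but sets significance at a two-sided p below 0.05.
- **Final model.** Later in the section: "The final models will include factors that remain significant at the 0.05 level". And: "All statistical tests will be two-sided with a significance level of 0.05".

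Reading these together, elimination runs to p<0.05 and the reported adjusted odds ratios are those of the variables left. The section mentions no shrinkage or validation step and does not call the analysis exploratory.

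**The concern.** The same 200 or so respondents choose the variables and then supply their odds ratios, intervals and p-values. A variable enters the final model only if its estimate in this sample is far enough from 1 to pass 0.05. For a weak or moderate association that happens mainly when chance has inflated the estimate, so what is reported overstates the association on average. Variables that miss the threshold have no adjusted estimate in the final model.

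At stake is how far readers can rely on the size of any factor said to go with better or worse HCV knowledge, for example when deciding where to direct patient education. No treatment decision and no other endpoint depends on it.

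Selection is also avoidable here. The nine variables are already named on subject-matter grounds, and the sample may be large enough to fit them together.

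**Working it through.** **Inputs from the protocol.** Nine candidates, screen at 0.20, backward likelihood-ratio elimination and the 0.05 level (section 7.4); 200 patients (section 7.3). The protocol gives no operating figure for the knowledge model, so there is none to reproduce. The interval in section 7.3 concerns diagnostic accuracy and has no bearing here.

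**Assumed, because the protocol does not give them.** Knowledge prevalence 50%; eight binary candidates and one continuous; latent correlation 0.3; one binary factor truly associated and eight not.

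**Step 1: why retention inflates an estimate.** Take a single balanced binary factor, so four cells of 50.
- SE of the log odds ratio ≈ √(1/50 + 1/50 + 1/50 + 1/50) = 0.283.
- To reach two-sided 0.05 the log odds ratio must exceed 1.96 × 0.283 = 0.554, an odds ratio of e^0.554 = 1.74.
- A true 1.5 therefore cannot be retained at its true size.

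The mean estimate given retention is β + SE × φ(a)/[1−Φ(a)], with a = (0.554 − β)/SE. The opposite tail is negligible.
- True OR 1.5 (β = 0.405): a = 0.526; retained in 1−Φ(a) = 30%; mean 0.405 + 0.283 × 0.347/0.299 = 0.733, OR 2.08.
- True OR 2.0 (β = 0.693): a = −0.491; retained in 69%; mean 0.693 + 0.283 × 0.354/0.688 = 0.838, OR 2.31.

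**Step 2: simulation of the full written rule** (n=200, geometric mean odds ratios).

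| True OR | Retained | Mean OR when retained | Mean OR, nine-variable model, always reported |
|---|---|---|---|
| 1.5 | 29% | 2.14 | 1.51 to 1.53 (two runs) |
| 2.0 | 66% | 2.40 | 2.08 |

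This agrees with Step 1. On the log scale the exaggeration is ln 2.14 / ln 1.5 = 0.761/0.405, about 1.9-fold, and ln 2.40 / ln 2.0 = 0.875/0.693, about 1.3-fold. Nominal 95% intervals from the nine-variable model covered the truth in 94-95% of studies. After selection, coverage was 92% at OR 1.5 and 96% at OR 2.0. For a variable with no true association that was nevertheless retained it was 2%, as expected when retention nearly requires the interval to exclude 1.

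**Step 3: false factors when nothing is associated.**
- Nine independent tests: 1 − 0.95^9 = 37.0%.
- Simulated written rule: about 38-39% in most settings, 35-40% across the correlations, codings and prevalences tried.
- Same simulated data, written rule against all nine variables fitted with no selection: 38.9% against 39.6%.
- Per variable under the rule: about 0.48 false factors per study / 9 = 5.3%.

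So the screen and elimination neither create nor reduce this rate.

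**Step 4: can nine variables be fitted?** At 30-50% prevalence, 200 respondents give 60 to 100 events. That is 60/9 = 6.7 to 100/9 = 11.1 per variable if each takes one parameter, and fewer per parameter with multi-category coding.

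**The case against.** Several points on the other side are sound.

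- **The error rate.** A reader might infer that the rule turns a promised 5% error into 37-39%. The protocol does not support that. It sets 0.05 per test and claims no familywise rate; the per-variable rate under the null is about 5.3%; and the nine-variable model without selection has the same chance of at least one p below 0.05.
- **The intervals.** A reader might also infer that all intervals after selection are too narrow. At true odds ratios of 1.5 and 2.0, coverage was 92% and 96%. Serious failure is confined to retained variables with no real association.
- **The comparison.** The retained mean is conditional on significance and the nine-variable mean is not. Quoting only the significant rows of a full model would bring the exaggeration back. The gain depends on reporting every estimate.
- **Feasibility.** The cut-point for knowledge, its prevalence and the coding of education, accommodation and employment are not given. HCV infection status may vary little: section 4.1 describes patients about to be treated, although section 4.2 requires only antibody. A nine-variable model could then be larger or less stable than assumed.
- **Weight.** This is a questionnaire association analysis in an observational cohort, with candidates and rule stated in advance. Stepwise selection is common in such work, and an exploratory label could sit in a statistical analysis plan that is not shown.

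What remains is that section 7.4 itself fixes the selection rule, and that rule distorts the odds ratios it reports. Calling the endpoint secondary does not answer this, because it concerns estimation and not control of type I error.

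**Conclusion.** The point holds as one of selection bias. Under the stated assumptions, a true odds ratio of 1.5 is reported as about 2.1 on average when retained, and a true 2.0 as about 2.4; the nine-variable model gives about 1.5 and 2.1. The exaggeration shrinks as the true association grows. These sizes depend on the assumed prevalence, correlation and coding, and on one true factor among nine. The direction follows from the rule itself.

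Severity is minor. SVR12, the diagnostic-accuracy estimates and the sample size are untouched, and nothing in the protocol is contradicted.

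**What to change.** In section 7.4, for the knowledge outcome only:

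- Replace the screen and backward elimination with one prespecified logistic model containing the nine named variables.
- Allow any variable with almost no variation to be dropped, or sparse categories collapsed, with that decision made without looking at the outcome.
- Report every adjusted odds ratio with its 95% CI, whatever its p-value.
- Describe the individual-factor results as exploratory.

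Do not make claims conditional on an overall likelihood ratio test. Such a gate guards only against the case where nothing is associated. With one true odds ratio of 3, a simulation gave at least one false factor in 32% of studies with the gate and 29% under the written rule.

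The cost is a few sentences and no new data. Some intervals will be somewhat wider, and the model will be larger relative to the data if knowledge is unbalanced or several variables have more than two categories.

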#### 8.0 Data Collection

The Principal Investigator and the institution where the study will be conducted will permit the collection of follow up data, study-related monitoring, audits, ethics committee review and regulatory inspection providing direct access to source documents.

All data collected will be entered into an electronic tablet or paper case report form. This will be managed by the data team at The Kirby Institute. Electronic data are on a password protected computer and data is stored on a secure server, which is backed up daily. Permission to access the dataset is only provided to individuals who are responsible for the data entry, upon completion of appropriate training from Kirby Institute staff. All required data collected must be complete, accurate and recorded in a timely manner by the site staff. The study questionnaires may act as the source document for the following study variables;

- Participant self-administered questionnaires
- Demographics

It is not acceptable for the study forms to be the only record of the participation in the study and the participant clinical data should also be recorded in the case notes.

The investigator and the institution where the study will be conducted will permit trial-related monitoring, audits and ethics committee review by providing direct access to the case notes.

The investigator is responsible for retaining all essential documents listed in ICH-GCP guideline. These should be organised in a comprehensive filing system that is accessible to study and other relevant personnel.

The investigator must retain all study documentation for 3 years following completion of the study. The investigator is responsible for ensuring that study records are not accidentally destroyed.

